12.3 Statistical methods and analytical procedures

Descriptive statistics will be used. The primary endpoint will be presented both as number and percentage, and by point estimates of the proportions combined with a two-sided 95% CI.

For secondary endpoints, the distribution of categorical and dichotomous variables will be presented both as number and percentage, although the composite variable will be presented as for the primary endpoint. Data will be presented for each time separately as well as across visits, where applicable. The distribution of continuous variables will be given as Mean, standard deviation (SD), Median, Minimum and Maximum.

For the safety endpoint, device deficiencies, adverse events and serious adverse events related to the device will be descriptively reported using frequency tables and listings.

All statistical analyses are to be explained in detail in a statistical analysis plan (SAP). Any deviations from the original analysis plan will be described in a CIP amendment, as deemed appropriate.

12.4 Missing data and special considerations

Missing data will not be imputed. For the primary endpoint, subjects withdrawn from the study due to loss of implant placed during the study (extrusion or elective removal) will be included in the analysis as a treatment failure (i.e. implant/abutment complex not in situ).

In case of any bilaterally implanted patient, implants will be handled as independent from each other for all implant-related variables, since this is considered more clinically relevant. Patient-variables such as patient characteristics and questionnaires will be presented on a patient-level.

No bias nor confounding factors are expected due to the single-arm design.

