8 OBJECTIVES AND ENDPOINTS

8.1 Primary objective

Primary objective	Corresponding primary endpoint/outcome variable(s)	Section
A. To investigate the proportion of Ponto implant/abutment complexes providing a reliable anchorage for a sound processor three months after MONO surgical procedure	1. Composite variable [Yes/No] including: I. Implant/abutment complex in situ II. Implant stability III. Absence of: a. Holgers score ≥ 2 , preventing use of sound processor b. Patient-reported pain preventing use of sound processor c. Skin overgrowth preventing use of sound processor	10.3.1

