10.3 Clinical investigation assessments

10.3.1 *Implant/abutment complex capability to provide a reliable anchorage for a sound processor after MONO surgical procedure*

The primary endpoint variable of this study ('capability to provide a reliable anchorage for a sound processor') is a composite variable depending on the outcome of five other variables:

- I. Implant in situ [Implant survival: No/Yes] (see section 10.3.2);
- II. Implant stable [Implant stability: No/Yes] (see section 10.3.3);
- III. Absence of:
 - a. adverse skin reaction (Holgers score ≥ 2) preventing use of sound processor [No/Yes] (see section 10.3.4.2);
 - b. pain preventing use of sound processor on implant/abutment complex [No/Yes] (see section 10.3.6);
 - c. skin overgrowth preventing use of sound processor on the implant/abutment complex [No/Yes] (see section 10.3.4.3)

For this composite endpoint to result in a positive outcome [=Yes], all involved variables need to be answered with [Yes]. If any involved variable is answered with [No], the outcome of the composite variable will be considered a failure [=No]. The rate of subjects (or implant/abutments complexes, if a subject is treated bilaterally) with a positive outcome will be used to calculate point estimates of the proportions with a two-sided 95% confidence interval. These point estimates and corresponding confidence intervals will be used to establish the expected level of implant/abutment complexes that are capable to provide a reliable anchorage (i.e. usage) for a sound processor, at the respective time point.

10.3.2 *Implant survival*

At each follow-up visit, the Investigator will assess whether the implant is still in situ (in place) by means of a [No/Yes] question. The rate of implant survival will be calculated from the number of

implants in situ over the number of implants that were placed. The rate of implant failure will be implicit. The reason for any failure (e.g. spontaneous, trauma etc.) will be documented.

10.3.3 *Implant stability*

Implant stability will be assessed by means of the subjective clinical judgement of the investigator. If the implant is firmly situated in the bone and assumed to be sufficiently osseointegrated when gently manipulating the implant/abutment using the fingers, it is judged stable [Yes]. If the implant is loose, with a lack of osseointegration, the implant is judged not stable [No].

10.3.4 *Skin assessments*

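### Section 10.3.1 scores component I of the primary composite on the implant alone, and 12.4 assigns no outcome to abutment-only removal or to early leavers whose implant is in place

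*Combined protocol and SAP*

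**What the plan says.** **Component I.** Section 8.1 defines the primary endpoint as "Composite variable [Yes/No] including: I. Implant/abutment complex in situ", followed by stability and the absence of three use-preventing problems. The synopsis and 8.2 agree. Section 10.3.1, which says how the composite is scored, lists instead "Implant in situ [Implant survival: No/Yes] (see section 10.3.2"). Section 10.3.2 asks only about the implant.

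**Composite rule.** Section 10.3.1 gives a positive result only when every item is Yes, and adds: "If any involved variable is answered with [No], the outcome of the composite variable will be considered a failure [=No"]. It has no rule for a blank item.

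**Missing data.** Section 12.4 states: "Missing data will not be imputed. For the primary endpoint, subjects withdrawn from the study due to loss of implant placed during the study" are scored as not having the complex in place, and so as failures, whether the implant came out by itself or was taken out by choice. It also says: "No bias nor confounding factors are expected due to the single-arm design".

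**Denominator and populations.** Implant survival has a stated denominator, "implants in situ over the number of implants that were placed". The primary composite has none. Section 12.1 defines ITT and per-protocol populations but ties neither to the primary endpoint. Section 9.4.4 says that withdrawn subjects are not replaced and that their data will be used where possible. Section 12.3 leaves analysis detail to a SAP.

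**The concern.** The 3-month proportion with its 95% CI is the main result, so its numerator and denominator need to be unambiguous. They are not in two situations.

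- **Abutment gone, implant in place.** Section 7.1.1 notes that the abutment can often be removed by itself. Such a complex cannot carry a processor, yet it meets component I as 10.3.1 words it.
- **Leaving before 3 months for pain or a skin problem, implant in place.** There is no 3-month composite, no imputation, and no failure rule that applies. The natural complete-case reading leaves the subject out.

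In both, the complexes at risk of being left out are more likely than average to be failures. A single-arm design does not prevent missingness that depends on outcome, so the reason given for expecting no bias does not support that conclusion.

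**Working it through.** **The plan's own figures.** The sample size rests on precision (12.2). The Wald formula is n = 4z²p(1−p)/w². With z = 1.96, p = 0.85 and w = 0.20 it gives 48.98, so 49 against the stated 50. At p = 0.95 and n = 50 the Wald limits are 88.96% and 101.04%. Cut at 100%, the width is 11.04 points, which matches the stated 11%. The sample size is not in question.

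**Case 1: abutment removed, implant left.**

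1. Component I: the 10.3.2 question is about the implant, so the literal answer is Yes.
2. Component II: the implant is stable if firm "when gently manipulating the implant/abutment using the fingers, it is judged stable [Yes"]. Without an abutment this cannot be done as written, so the item is probably blank.
3. Composite: one blank means that not every item is Yes. If no item is No, the failure rule is not met either. The most likely result is blank. It is Yes only if stability is recorded contrary to 10.3.3.
4. The failure rule in 12.4 needs withdrawal for loss of the implant. Abutment-only removal is neither that nor a withdrawal criterion in 9.4.4.

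**Case 2: early leaver, implant and abutment in place.** The event would be visible: 9.4.4 records the reason for withdrawal, 19.5 documents withdrawals due to adverse events, and Table 4 allows assessments at unscheduled visits. None of these assigns a score. The items on prevented use may also be unanswered, because fitting can be as late as the 3-month visit (Table 4) and 10.3.6 asks the pain item only where applicable.

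**Size.** The CIP gives no withdrawal or abutment-removal rate, so I assume k = 0 to 3 cases among 50 single implants. S is the number of successes if all were observed.

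- Dropped cases are true failures: shift = S/(50−k) − S/50.
  - S = 42: +1.71, +3.50, +5.36 points for k = 1, 2, 3.
  - S = 47: +1.92, +3.92, +6.00 points.
- Dropped cases would have succeeded: shift = (S−k)/(50−k) − S/50.
  - S = 42: −0.33, −0.67, −1.02 points.
  - S = 47: −0.12, −0.25, −0.38 points.
- k = 0: no shift.

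Clopper-Pearson 95% intervals for k = 1 with a true failure dropped:

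- 42/50 = 84.0% (70.9–92.8) becomes 42/49 = 85.7% (72.8–94.1).
- 47/50 = 94.0% (83.5–98.7) becomes 47/49 = 95.9% (86.0–99.5).

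The untruncated Wald half-widths at n = 50 are about 9.9 points at 85% and 6.0 at 95%, so one case lies well inside them. The +6.00 extreme is 47/50 to 47/47, where every failure in the study is a leaver.

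**The case against.** Much of the text points to scoring the complex as a whole: the title and closing sentence of 10.3.1, the reference to loadable complexes in 12.2, and 12.4's own gloss on implant loss. On that view the wording of component I is a slip. Denominators and blank items are ordinary SAP content, 12.3 promises a SAP, and not imputing is a legitimate choice in a descriptive study. The size is wholly assumed.

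Some of this stands, and it rules out stronger readings that a reader might infer:

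- **That any complex that has stopped working escapes.** It does not. At the 3-month visit a loose implant fails component II, and use-preventing skin reaction, pain or overgrowth fails component III.
- **That a complex without an abutment would count as a success.** That needs a stability Yes which 10.3.3 hardly allows. Blank is the likelier result.
- **That the trial as a whole has no denominator.** The SAP may state one, and the CIP alone cannot show otherwise.
- **That every early withdrawal for pain or skin problems is a failure.** Section 7.1.1 expects temporary pain during healing, so an early problem does not establish a 3-month failure.

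What does not fall is the conflict between 8.1 and 10.3.1, which lies within the CIP, and the missing-data rule that 12.4 has already fixed there. The general statement in 9.4.4 about using collected data assigns no score.

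**Conclusion.** The point holds in a limited form and should be fixed before the 3-month analysis. Two kinds of case have no assigned outcome in the CIP: abutment removed with the implant in place, and departure before 3 months for a reason other than implant loss. Leaving them out tends to raise the success rate, because a dropped failure moves it by 1.7 to 1.9 points and a dropped success by 0.1 to 0.3 the other way. This rests on assumed counts, 50 single implants, and a complete-case reading of 12.4. With no such cases nothing changes; with one, the shift is small against the interval. The study tests no hypothesis and sets no success threshold, so only the estimate and its interval are affected.

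**What to change.** 1. **Section 10.3.1.** Score component I as Yes only if implant and abutment are both in place at the time point, and record each in the eCRF. State that any No makes the composite No even when other items are blank. Leave implant survival in 10.3.2 unchanged.
2. **Section 12.4, scoring.** Keep the failure rule for implant loss for all subjects, fitted or not. Extend it to removal or loss of the abutment before 3 months.
3. **Section 12.4, denominator.** State that the primary proportion covers complexes in the ITT population with an observed or so-assigned 3-month outcome. Report the number missing with the recorded withdrawal reasons.
4. **Supporting figures, with 95% CIs.** Over all implants placed in the ITT population, give a worst case (all missing are failures) and a best case (all missing are successes). As a sensitivity analysis, count as failures the leavers whose recorded reason matches a component of the composite, fitted or not.
5. **The sentence expecting no bias.** Delete or qualify it.

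Illustration with assumed counts: 50 implants, 43 Yes, 4 No, and 3 leavers with implant and abutment in place, 1 of them with a matching reason.

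- Primary: 43/47 = 91.5% (79.6–97.6), 3 missing.
- Sensitivity: 43/48 = 89.6% (77.3–96.5).
- Worst case: 43/50 = 86.0% (73.3–94.2).
- Best case: 46/50 = 92.0% (80.8–97.8).

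The cost is CIP and SAP wording, one or two eCRF items, a little more analysis, and possibly a slightly lower reported rate. Withdrawal reasons are already collected.

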9.4.4 Criteria and procedures for subject withdrawal or lost to follow up

Subjects are free to discontinue participation in the investigation at any time without affecting the medical care of the subject. If a subject withdraws from the clinical investigation, the reason(s) shall be recorded. If such withdrawal is due to problems related to the investigational device safety or performance, the investigator shall ask for the subject's permission to follow his/her status/condition outside the clinical investigation.

Withdrawal criteria:

- Unwillingness to continue participation in the study
- Loss of implant placed during the study (extrusion or elective removal)
- Patients lost to follow-up (following three documented contact attempts)

Subjects withdrawing from the investigation after implantation will not be replaced. Collected data will be considered as far as possible in analyses.

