12 STATISTICAL DESIGN AND ANALYSIS

12.1 Study design and analysis populations

The investigation is a multinational, multicentre, prospective, single-arm investigation to establish the level of successful implant/abutment complex installations using the MONO surgical procedure. Fifty patients will be included to prospectively study the proportion of implant/abutment complexes that are performing as intended (thus capable of providing a reliable anchorage for the sound processor) three months after using the MONO surgical procedure.

Three analysis populations will be defined in the investigation, i.e. safety-, intention-to-treat- (ITT) and per-protocol- (PP) analysis populations. The data used for the safety-population analysis will include relevant safety data from all consenting subjects in the study. The ITT population will include all subjects undergoing surgery in the investigation. The PP population will include treated subjects that do not have any significant protocol deviation.

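### No outcome rule or bound for operated patients whose composite is missing for reasons other than implant loss, and no implant-loss rule at 6 and 12 months

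*Combined protocol and SAP*

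**What the plan says.** - **Missing data (Section 12.4).** The general rule is "Missing data will not be imputed". The single exception is introduced as applying to the primary endpoint and concerns subjects withdrawn because a study implant was lost: "extrusion or elective removal) will be included in the analysis as a treatment failure (i.e. implant/abutment complex not in situ".
- **Withdrawal (Section 9.4.4).** Implant loss is one of three withdrawal criteria. The other two are the subject no longer wishing to take part and "Patients lost to follow-up (following three documented contact attempts"). Neither has an outcome attached. Further, "Subjects withdrawing from the investigation after implantation will not be replaced", and "Collected data will be considered as far as possible in analyses".
- **Analysis sets (Section 12.1).** "The ITT population will include all subjects undergoing surgery in the investigation". A per-protocol set and a safety set are also defined. The section does not say which set carries the primary estimate.
- **Estimator (Section 10.3.1).** "The rate of subjects (or implant/abutments complexes, if a subject is treated bilaterally) with a positive outcome will be used to calculate point estimates". How a complex with an unknown composite enters the calculation is not stated. Only implant survival (Section 10.3.2) has an explicit denominator: "implants in situ over the number of implants that were placed".
- **Later time points (Section 8.2, objective B).** The same composite is a secondary endpoint at 6 and 12 months.

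**The concern.** Implant loss is only one way to fail. Under Section 10.3.1 a complex also fails if it is unstable, or if a Holgers score of 2 or more, pain or skin overgrowth prevents use of the sound processor. A patient who withdraws because of pain or a skin problem, or who simply stops attending, is outside the exception in Section 12.4. Without imputation, and without a rule that assigns an outcome, the natural reading is that this patient is left out of the proportion. If such patients fail more often than those assessed, the reported success rate is too high, and its 95% CI does not show this.

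The later composites have a further gap. Implant loss triggers withdrawal, so a patient whose implant was lost has no 6- or 12-month visit. The rule that would turn that known loss into a failure is written for the primary endpoint only. Read literally, a known failure becomes missing data that is not imputed.

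The study's product is an estimate of the level of successful installations. An undefined denominator therefore bears directly on its main result.

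**Working it through.** **The plan's own figure.** Section 12.2 gives 50 patients for a total 95% CI width of 20 points at 85% success. With n = z²p(1−p)/h², z = 1.96, p = 0.85 and h = 0.10, n = 48.98, so 49. The stated 50 is reproduced. It contains no stated allowance for missing outcomes. The simple normal-approximation width at 85% is 19.8 points for n = 50, 20.4 for n = 47 and 20.9 for n = 45, so the loss of precision is small. The question is bias.

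**Inputs.** N = 50 operated patients (Sections 9.4.3 and 12.2). Success near 85% (the rate that sets N) and near 95% (the second scenario in Section 12.2). The number m with an unknown 3-month composite is an assumption, shown from 1 to 10, with one implant per patient.

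**Formulas.** With x observed successes:
- observed-case: x/(N − m)
- missing = failure: x/N
- missing = success: (x + m)/N
- distance between the two bounds: m/N, i.e. 2 points per missing patient
- observed-case minus missing = failure: [x/(N − m)] × (m/N), so never more than 2 points per missing patient

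**Results** (exact 95% CI in brackets; the plan names no CI method).

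| Scenario | m | Observed-case | Missing = failure | Missing = success |
|---|---|---|---|---|
| near 95% | 1 | 47/49 = 95.9% (86.0–99.5) | 47/50 = 94.0% (83.5–98.7) | 48/50 = 96.0% (86.3–99.5) |
| near 95% | 3 | 45/47 = 95.7% (85.5–99.5) | 45/50 = 90.0% (78.2–96.7) | 48/50 = 96.0% (86.3–99.5) |
| near 95% | 5 | 43/45 = 95.6% (84.9–99.5) | 43/50 = 86.0% (73.3–94.2) | 48/50 = 96.0% (86.3–99.5) |
| near 95% | 10 | 38/40 = 95.0% (83.1–99.4) | 38/50 = 76.0% (61.8–86.9) | 48/50 = 96.0% (86.3–99.5) |
| near 85% | 1 | 42/49 = 85.7% (72.8–94.1) | 42/50 = 84.0% (70.9–92.8) | 43/50 = 86.0% (73.3–94.2) |
| near 85% | 3 | 40/47 = 85.1% (71.7–93.8) | 40/50 = 80.0% (66.3–90.0) | 43/50 = 86.0% (73.3–94.2) |
| near 85% | 5 | 38/45 = 84.4% (70.5–93.5) | 38/50 = 76.0% (61.8–86.9) | 43/50 = 86.0% (73.3–94.2) |
| near 85% | 10 | 34/40 = 85.0% (70.2–94.3) | 34/50 = 68.0% (53.3–80.5) | 44/50 = 88.0% (75.7–95.5) |

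The observed-case figure lies close to the upper bound because the observed success rate is high. Almost all the uncertainty from missing outcomes is therefore downward.

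**Implant loss at 6 and 12 months.** Take, as an assumption, one implant lost among 50 (the 98% survival quoted in Section 6.1 would give 0.02 × 50 = 1), with all others successful. Counting the loss gives 49/50 = 98.0%; dropping it gives 49/49 = 100%. Here the outcome is known, so the 2-point difference would be an error of counting rather than an uncertainty.

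**The case against.** A reader might infer that the primary result is an intention-to-treat estimate from which patients silently disappear. The documents do not support that.

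- **No set is assigned.** Section 12.1 defines the sets but none is tied to the primary proportion. Leaving the denominator is the natural reading of Sections 12.4 and 10.3.1, but it remains an inference.
- **It would not be silent.** Section 9.4.4 requires reasons for withdrawal to be recorded, and Section 12.3 requires numbers as well as percentages. If a report gives successes, number assessed and number operated, a reader can work out the bounds.
- **The most clearly outcome-related withdrawals are handled.** Implant loss counts as failure at 3 months.
- **Informative dropout is not shown.** Nothing in the protocol indicates that patients who cannot use the processor stop attending. Visits largely follow routine care, fitting takes place by the 3-month visit at the latest, and loss to follow-up requires repeated contact attempts.
- **Detail is deferred.** Section 12.3 leaves the full analysis to a SAP, and no separate SAP text is in the documents available. Section 12.3 also says that the later composite is presented like the primary one, which might be meant to carry the failure rule along.

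Most of this stands, and it limits the point to a missing rule and a missing bound. It does not close the gap. Section 12.4 already fixes the no-imputation rule, and a SAP would have to add to it. The sentence in Section 12.3 concerns presentation, not classification of withdrawn subjects. Section 12.4 also says that no bias is expected because the design is single-arm, but that does not address attrition.

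A second tempting reading is that missing outcomes would outweigh the observed failures. With 3 or 5 missing, that holds near 95% (two observed failures). It does not hold at the 85% planning rate, where each row up to m = 5 has seven observed failures.

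**Conclusion.** The point holds in a limited form. For operated patients whose 3-month composite is unknown for a reason other than implant loss, the protocol gives no classification, no denominator and no bounding analysis. For the 6- and 12-month composites, the implant-loss rule does not literally apply either.

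The effect depends on a number that the documents do not give. If all missing patients had failed, the observed-case estimate would be too high by 5.7 points (3 missing) or 9.6 points (5 missing) near 95% success, and by 5.1 or 8.4 points near 85%. These are extreme bounds, not estimates of a likely bias. If missing patients resemble those assessed, there is no bias; with one missing the difference is at most 2 points, and with none it is zero. Bilateral implants would raise the denominator above 50 and change these figures slightly. The study is descriptive with no performance threshold, so no pass/fail decision turns on this. It is an inexpensive improvement that should be made, not a demonstrated flaw in an intention-to-treat analysis.

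**What to change.** In Section 12.4, and in the SAP:

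1. Name all implant/abutment complexes placed in operated subjects as the primary analysis set, and state the denominator of each estimate.
2. Keep the observed-case proportion, with implant loss counted as failure, as the main estimate.
3. Extend the implant-loss-as-failure rule explicitly to the 6- and 12-month composites.
4. Prespecify two bounds on all placed complexes, missing = failure and missing = success, with the same 95% CI method, at 3, 6 and 12 months.
5. Report the number with an unknown composite and the reasons at each time point.

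This adds a few table rows and requires no new data, visits or patients. The only downside is that the worst-case figure will be less favourable than the observed-case one.
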